# 6.4.2 Clinical Laboratory Evaluations

Clinical laboratory data (i.e., serum chemistry, hematology evaluations including CBC with differential and platelet counts, urinalysis values) will be summarized by descriptive statistics by treatment group at the end of the final follow-up visit (Week *153*).

# 6.4.3 MRI Evaluations

Neuroradiologic evaluation with respect to the occurrence of cerebral vasogenic edema, superficial siderosis of central nervous system, and cerebral micro- or macrohemorrhages will be performed during the *153*-week study period and will be summarized by treatment group using descriptive statistics.

# 6.4.4 Anti-Therapeutic Antibodies

The number and percentage of patients with confirmed positive ATA levels will be reported for each treatment group at the end of the final follow-up visit (Week *153*).

# 6.5 PHARMACODYNAMIC ANALYSES

Exploratory PD biomarkers will be evaluated in plasma samples collected at specified visits indicated in the study flowchart (see Appendices A1 and A2) and will consist of Abeta species as well as other plasma markers implicated in Alzheimer's disease progression. Individual and mean plasma total Abeta1-40 and Abeta1-42 concentrations versus time data will be tabulated and plotted by dose level.

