#### Crenezumab—Genentech, Inc.

there appears to be a trend towards reduction in cognitive decline in patients who received 15 mg/kg q4w IV. Considering these efficacy results and the available safety information, all patients in the OLE study will be dosed at 15 mg/kg q4w IV. All patients who have been receiving active drug in the SC dosing arm will be transferred into the IV dosing arm.

The study consists of three periods: a screening period (up to 14 days), the window between the last dose in ABBY/BLAZE and the first dose in OLE may last 6 weeks, but may be prolonged on a case by case basis for relevant clinical, administrative, or operational reasons (these reasons must be discussed with the medical monitor in advance of screening; if necessary, some screening procedures may need to be repeated); period of 144 weeks (Week 1 [Day 1] to Week 145), and an 8-week safety follow-up period (Weeks 145 to 153). The final safety analysis will be performed at 153 weeks. The original GN28525 protocol included a treatment period of 92 weeks (Week 1 [Day 1] to Week 93). Version 6 of the GN28525 protocol expands this treatment period by 52 weeks (13 additional IV doses from Week 97 to Week 145). Patients who are still enrolled in Study GN28525 may enter the additional OLE treatment period (Week 97 to Week 145) if they have not discontinued treatment for safety reasons. Patients who have already completed or discontinued from Study GN28525 are not eligible to receive additional treatment from Week 97 to Week 145.

The Week 73 assessment (including MRI) of Studies ABE4869g and ABE4955g will be used to determine the patient's eligibility in this OLE trial. Data from the Week 73 visit assessments in Studies ABE4869g and ABE4955g will be extracted and incorporated in the OLE screening datasets. Patients participating in this OLE study must be enrolled (i.e., Day 1 of the OLE treatment period) no later than 14 days after completion of the Week 73 assessments (including MRI) of Study ABE4869g or ABE4955g, except for individual exceptions, determined on a case by case basis, as mentioned above.

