## 1.3.3.5 Additional Safety Information

In the ongoing OLE study (GN28525) as of 27 May 2014, three deaths occurred (additional details above). As of 27 May 2014, serious adverse events were reported in 15 SC patients (10.1%) and 18 IV patients (8.5%). Eight SC patients (5.4%) and 2 IV patients (0.9%) discontinued treatment due to an adverse event. Asymptomatic ARIA-E was reported in 1 IV patient (0.5%; the same patient with ARIA-E in ABE4869g) and no SC patients. Superficial siderosis was reported in one SC patients (0.7%) and no IV patients. No macrohemorrhages were reported in SC or IV patients. Incident asymptomatic microhemorrhages were reported in 6 SC patients (4.1%) and 3 IV patients (1.4%).

Additional safety information for the ABE4869g, ABE4955g, GN28525, and GN28352 studies are provided in the Investigator's Brochure.

Based on a review of Phase II safety data to date, while imbalances in deaths and pneumonia were observed in the RPCP, a drug-related causal relationship has not been established. New fatalities in the ongoing OLE study (GN28525) will be closely monitored, and exposure-adjusted fatality rates using the total-person time on crenezumab treatment will be compared to expected rates from published data.

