## 1.3.4 Clinical Pharmacokinetics

The pharmacokinetics of crenezumab have been evaluated in two Phase I studies (ABE4427g and ABE4662g) and in the two Phase II studies (ABE4869g and ABE4955g) and will be further assessed upon completion of the ongoing, OLE study (GN28525) and the Phase II study (GN28352) in PSEN1 E280A mutation carriers. Overall, the observed clearance and volume of distribution in the Phase I studies are consistent with those for other humanized IgG monoclonal antibodies that exhibit kinetics in the linear concentration range (Mould and Sweeney 2007; Dirks and Meibohm 2010; Deng et al. 2011).

In Study ABE4427g, crenezumab was given either as a single (0.3–10 mg/kg) or weekly (0.5–5 mg/kg) IV bolus to patients with mild-to-moderate Alzheimer's disease. Following single-dose administration, crenezumab pharmacokinetics were characterized by linear exposure across the dose range tested, slow clearance (2.5–3.3 mL/day/kg) and a long half-life (17–26 days). With weekly administration, there did not appear to be any time-dependent change in crenezumab kinetics, as evidenced by similar terminal elimination half-life estimates (18–23 days) relative to the single-dose arm.

In the Phase II studies (Study ABE4869g and Study ABE4955g), serum crenezumab concentrations were measured in samples collected after bi-weekly SC (300 mg every 2 weeks [q2w]) or monthly IV (15 mg/kg every 4 weeks [q4w]) administration in patients with mild-to-moderate Alzheimer's disease. In general, serum pharmacokinetic (PK) concentrations were similar between the two Phase II studies. In Study ABE4869g, after 68 weeks of dosing with SC (q2w) or IV (q4w) crenezumab, mean (standard deviation; SD) steady state trough serum crenezumab levels were 69 (30)  $\mu$ g/mL and 118 (72)  $\mu$ g/mL, respectively. For patients in the IV and SC treatment groups, steady-state trough serum crenezumab levels appeared to have been attained between Week 13 and Week 25 (after 3–6 doses of IV or 6–12 doses of SC) in both studies. The trough crenezumab levels in cerebrospinal fluid (CSF) were measured in a subset of patients in ABE4869g and in all patients in ABE4955g at Week 69. In preliminary analysis of CSF crenezumab concentrations, penetration into CSF was similar between the two studies as well as between the SC and IV doses. In study ABE4869g, the mean (SD) CSF/serum ratio was 0.26% (0.16%) and 0.28% (0.17%) for IV and SC dosing, respectively.

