patients with 4 or less cerebral microhemorrhages at screening are allowed to participate in Studies ABE4869g and ABE4955g and study drug will be discontinued in patients with an increase of six or more in the number of asymptomatic microhemorrhages in these studies since high numbers of cerebral microhemorrhages have been associated with future risk of ischemic and hemorrhagic strokes (Greenberg et al. 2009). The microhemorrhage threshold for entry in this study, which is based on the natural incidence of cerebral microhemorrhages in this patient population, is intended to minimize potential safety risks associated with cerebral microhemorrhages, but would not preclude the majority of the patients from Study ABE4869g or ABE4955g from rolling over into this OLE study. However, this might exclude patients from participating in the OLE study due to the number of cerebral microhemorrhages that would not have led to treatment discontinuation in the Study ABE4869g or ABE4955g. Patients with medical or psychiatric contraindication or clinically significant abnormalities that, in the investigator's judgment, would substantially increase the risk associated with the patient's participation in the study or interfere with the evaluation of the patient's response will not be included in the study.

All patients enrolled in the OLE study were to receive active drug at the same dosing frequency, dose level, and route of administration they were assigned to after the Week 73 visit of Study ABE4869g or ABE4955g. Patients who received matching placebo in Study ABE4869g or ABE4955g were to receive active drug (i.e., crenezumab 300 mg SC q2w for patients who were randomized in the SC cohort [Part 1] or 15 mg/kg IV q4w for patients who were randomized in the IV cohort [Part 2]). However, evaluation of efficacy in ABE4869g and ABE4955g indicates that there was no consistent treatment effect in patients who received 300 mg q2w SC that would support continuation of this dose level. In contrast, there appears to be a trend towards reduction in cognitive decline in patients who received 15 mg/kg q4w IV. Considering these efficacy results and the available safety information, all patients in the OLE study will be dosed at 15 mg/kg q4w IV. All patients who have been receiving active drug in the SC dosing arm will be transferred into the IV dosing arm.

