# 4.2 METHOD OF TREATMENT ASSIGNMENT AND BLINDING

This is an OLE study. Patients in the OLE study will receive study drug at 15 mg/kg IV q4w. Patients who received active drug in Study ABE4869g or ABE4955g will continue to receive active drug. Patients who received placebo in Study ABE4869g or ABE4955g will also receive active drug (i.e., crenezumab 15 mg/kg IV q4w).

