# 6.6 PHARMACOKINETIC ANALYSES

Individual and mean serum crenezumab concentration versus time data will be tabulated by dose level, and Ctrough, ss will be reported. Parameters will be tabulated and summarized (e.g., mean, standard deviation, minimum, and maximum). Additional PK analyses may be conducted as appropriate.

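### PK and Abeta means grouped by dose level alone mix crenezumab-naive with pre-treated patients early in the extension and leave SC-to-IV switchers without a group or time origin

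*Combined protocol and SAP*

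**What the plan says.** Section 6.5 names one grouping for the Abeta summaries: "Individual and mean plasma total Abeta1-40 and Abeta1-42 concentrations versus time data will be tabulated and plotted by dose level". Section 6.6 does the same for drug levels: "Individual and mean serum crenezumab concentration versus time data will be tabulated by dose level". It also promises the steady-state trough (Ctrough,ss) without defining which samples count.

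Section 4.2 states that "Patients in the OLE study will receive study drug at 15 mg/kg IV q4w", and adds that patients who had placebo in Study ABE4869g or ABE4955g get this same regimen. Section 3.1.1 explains that the SC cohort was first to receive active drug at 300 mg SC q2w in the OLE, former placebo patients included, and then says "All patients who have been receiving active drug in the SC dosing arm will be transferred into the IV dosing arm".

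Section 6.4 groups patients by both OLE and feeder-study assignment, but under the heading of safety analyses. Sections 6.5 and 6.6 do not repeat that grouping. Section 6.7 refers analyses of the exploratory objectives to a Statistical Analysis Plan; the text available contains none beyond Section 6.

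**The concern.** A mean concentration-time curve is interpretable when the patients averaged at each time point have a comparable exposure history. Here they do not. Former placebo patients enter with no drug on board. Former IV-active patients enter at or somewhat below their steady-state trough. SC-origin patients change regimen part-way through, with feeder mean steady-state troughs of 69 µg/mL on SC against 118 µg/mL on IV (Section 1.3.4). Dose level separates none of these histories within a regimen, and nothing says where a switcher's data belong or whether the clock restarts at the switch.

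The PK and PD characteristics of crenezumab, and the PK/PD relationship, are stated exploratory objectives (Section 2.3). The former placebo patients are the group in which an off-drug to on-drug change can be seen within the OLE itself. Averaging them with patients already on drug blurs that change. It also treats the active-origin patients' Day 1 Abeta as though it were an off-drug starting value.

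**Working it through.** **Inputs**
- Mean IV steady-state trough 118 µg/mL (SD 72) in ABE4869g, and single-dose half-life 17–26 days from Phase I: Section 1.3.4.
- Last feeder dose on the first day of Week 69: Section 1.3. OLE Day 1 within 14 days of the Week 73 assessments, exceptions allowed: Section 3.1.1. The usual gap is therefore 28–42 days.
- Feeder exposure: 346 crenezumab and 176 placebo patients, randomised 2:1: Section 1.3.3. Placebo share 176/(346+176) = 176/522 = 33.7%. The split among OLE entrants is not given, so one third is assumed.
- OLE serious adverse events at 27 May 2014: 15 SC patients (10.1%) and 18 IV patients (8.5%): Section 1.3.3.5. These imply 15/0.101 ≈ 148 SC and 18/0.085 ≈ 212 IV patients, so a substantial SC phase exists in the OLE data.

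**Model.** One-compartment linear accumulation with dosing every 28 days; h is the half-life and n the number of OLE doses already given.
- Naive trough = 118 × (1 − 2^(−28n/h)).
- Pre-treated Day 1 level C0 = 118 × 2^(−(gap−28)/h).
- Pre-treated trough = naive trough + C0 × 2^(−28n/h). The last term is the difference between the groups.

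**Check against the protocol's own figure.** Section 1.3.4 says "steady-state trough serum crenezumab levels appeared to have been attained between Week 13 and Week 25", that is, after 3 to 6 IV doses. The model gives 89–97% of steady state after 3 doses and 99–100% after 6, so the stated half-life and the stated window agree.

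**Day 1, IV cohort**
- Gap of 4 weeks: C0 = 118.
- Gap of 6 weeks: C0 = 118 × 2^(−14/17) = 66.7, or 118 × 2^(−14/26) = 81.2; that is 57–69% of the steady-state trough.
- Pooled with two thirds pre-treated: 66.7 × 2/3 = 44 to 118 × 2/3 = 79 µg/mL.

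**Course over the OLE** (µg/mL, range over half-life 17–26 days and gap 4–6 weeks)

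| Visit | Doses given | Naive | Pre-treated | Pooled | Difference between groups |
|---|---|---|---|---|---|
| Day 1 | 0 | 0 | 67–118 | 44–79 | 67–118 |
| Week 5 | 1 | 62–80 | 101–118 | 88–105 | 21–56 |
| Week 9 | 2 | 92–106 | 110–118 | 104–114 | 7–27 |
| Week 13 | 3 | 105–114 | 114–118 | 111–117 | 2–13 |
| Week 25 | 6 | 117–118 | 118 | 117–118 | at most about 1 |

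The Week 13 limits, for example, are 66.7 × 2^(−84/17) = 2.2 and 118 × 2^(−84/26) = 12.6.

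**Abeta.** The documents give no time course of plasma Abeta after dosing, so no corresponding calculation is possible.

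**The case against.** The strongest reply is that dose level has not lost its meaning. A reader might infer from Section 4.2 that every patient in the dataset sits at a single dose level. The documents do not support that: SC patients received active SC drug in the OLE before transfer, so for much of the early period the grouping does separate the two regimens. This stands, but it does not remove the problem. Naive and pre-treated patients are mixed within the SC level as well as the IV level, and switchers still lack a rule.

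Second, Section 6.7 points to a Statistical Analysis Plan that may stratify by feeder arm, and Section 6.6 allows additional PK analyses. That is possible, but Sections 6.5 and 6.6 set their own grouping, and it should agree with whatever the plan does.

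Third, individual data are tabulated, nothing is tested, and no decision depends on these curves. All true, and it keeps the point minor. Individual listings do not, however, make a mixed mean curve informative.

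Fourth, the groups converge quickly. By Week 13 the difference is 2–13 µg/mL, against a between-patient SD of 72. This stands, and a Ctrough,ss taken after that time on an unchanged regimen is little affected. The sampling schedules are not in the text available, so how many samples fall in the affected weeks is unknown.

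**Conclusion.** The point holds as a minor one. As written, the mean PK and Abeta summaries average patients with different exposure histories, and SC-to-IV switchers have no assigned dose level or time origin. For IV-cohort PK the effect is large on Day 1 (0 against 67–118 µg/mL, pooled about 44–79), small by Week 13 and negligible by Week 25.

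These figures assume linear one-compartment kinetics, the Phase I half-life, the ABE4869g mean trough, a 4–6 week gap and the feeder placebo share carried into the OLE. A longer gap, which the protocol allows case by case, would lower the pre-treated Day 1 value.

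Three stronger inferences are not supported:
- That all pre-treated patients start at steady state. After six weeks IV patients would be at about 57–69% of it, and SC-origin patients come from a lower exposure.
- That pooling hides the entire Abeta onset, or that active-origin patients would show no Abeta response. Without an Abeta time course neither can be judged.
- That the curves are materially distorted right up to Week 25. The difference has largely gone by Week 13.

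The primary safety analysis has its own grouping in Section 6.4 and is not touched.

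**What to change.** In Sections 6.5 and 6.6:
1. Replace the dose-level grouping with feeder-study assignment (placebo or active; SC or IV cohort) and OLE regimen, in line with Section 6.4.
2. Show results by time since first crenezumab dose and, for SC-origin patients, also by time since the SC-to-IV switch. State to which regimen each switcher's samples belong.
3. Define Ctrough,ss as taken from samples after the protocol's own steady-state window (Week 13–25), counted on the current regimen.
4. Label Day 1 Abeta in active-origin patients as an on-drug value. Use the feeder pre-treatment value as reference where one exists; the text does not document feeder plasma Abeta sampling, so this needs confirming. For former placebo patients, use the value before their first active dose.

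If the separate Statistical Analysis Plan already does this, bring the protocol wording into line with it. The cost is a few sentences and regrouped tables and plots, with no new sampling. The downside is fewer patients per curve.

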# 6.6 PHARMACOKINETIC ANALYSES

Individual and mean serum crenezumab concentration versus time data will be tabulated by dose level, and Ctrough, ss will be reported. Parameters will be tabulated and summarized (e.g., mean, standard deviation, minimum, and maximum). Additional PK analyses may be conducted as appropriate.

# 6.7 EXPLORATORY ANALYSES

Refer to the Statistical Analysis Plan for analyses related to the exploratory objectives.

# 6.8 INTERIM ANALYSES

No interim analysis is planned for this study.

# 7. DATA COLLECTION AND MANAGEMENT

# 7.1 DATA QUALITY ASSURANCE

A contract research organization (CRO) will be responsible for the data management of this study, including quality checking of the data. Data entered manually will be collected via electronic data capture (EDC) using eCRFs. Sites will be responsible for data entry into the EDC system. In the event of discrepant data, the CRO will request data clarification from the sites, which the sites will resolve electronically in the EDC system.

The Sponsor will perform oversight of the data management of this study, and produce an EDC Study Specification document that describes the quality checks to be performed on the data. Central laboratory data and central imaging data will be sent directly to Genentech, using Genentech's standard procedures to handle and process the electronic transfer of these data.

eCRFs and correction documentation will be maintained in the EDC system's audit trail. System backups for data stored by the Sponsor and record retention for the study data will be consistent with the Sponsor's standard procedures.

# 7.2 ELECTRONIC CASE REPORT FORMS

eCRFs are to be completed using a Sponsor-designated EDC system. 'Sites will receive training and a have access to a manual for appropriate eCRF completion. eCRFs will be submitted electronically to the Sponsor and should be handled in accordance with instructions from the Sponsor.

All eCRFs should be completed by designated, trained site staff. eCRFs should be reviewed and electronically signed and dated by the investigator or a designee.

At the end of the study, the investigator will receive patient data for his or her site in a readable format on a compact disc that must be kept with the study records. Acknowledgement of receipt of the compact disc is required.

# 7.3 SOURCE DATA DOCUMENTATION

Study monitors will perform ongoing source data verification to confirm that critical protocol data (i.e., source data) entered into the eCRFs by authorized site personnel are accurate, complete, and verifiable from source documents.

Source documents, paper or electronic, are those in which patient data are recorded and documented for the first time. They include, but are not limited to, hospital records, clinical and office charts, laboratory notes, memoranda, patient-reported outcomes, evaluation checklists, pharmacy dispensing records, recorded data from automated instruments, copies of transcriptions that are certified after verification as being accurate and complete, microfiche, photographic negatives, microfilm or magnetic media, X-rays,

patient files, and records kept at pharmacies, laboratories, and medico-technical departments involved in a clinical trial.

Before study initiation, the types of source documents that are to be generated will be clearly defined in the Trial Monitoring Plan. This includes any protocol data to be entered directly into the eCRFs (i.e., no prior written or electronic record of the data) and considered source data.

Source documents that are required to verify the validity and completeness of data entered into the eCRFs must not be obliterated or destroyed and must be retained per the policy for retention of records described in Section 7.5.

To facilitate source data verification, the investigators and institutions must provide the Sponsor direct access to applicable source documents and reports for trial-related monitoring, Sponsor audits, and IRB/EC review. The investigational site must also allow inspection by applicable health authorities.

# 7.4 USE OF COMPUTERIZED SYSTEMS

When clinical observations are entered directly into an investigational site's computerized medical record system (i.e., in lieu of original hardcopy records), the electronic record can serve as the source document if the system has been validated in accordance with health authority requirements pertaining to computerized systems used in clinical research. An acceptable computerized data collection system allows preservation of the original entry of data. If original data are modified, the system should maintain a viewable audit trail that shows the original data as well as the reason for the change, name of the person making the change, and date of the change.

# 7.5 RETENTION OF RECORDS

Records and documents pertaining to the conduct of this study and the distribution of IMP, including eCRFs, ePRO data (if applicable), Informed Consent Forms, laboratory test results, and medication inventory records, must be retained by the Principal Investigator for at least 15 years after completion or discontinuation of the study, or for the length of time required by relevant national or local health authorities, whichever is longer. After that period of time, the documents may be destroyed, subject to local regulations.

No records may be disposed of without the written approval of the Sponsor. Written notification should be provided to the Sponsor prior to transferring any records to another party or moving them to another location.

